#### **6.3.2. Additional considerations**

The ANOVA model for the lot-to-lot GMC ratio will include the data from the 3 HRV liquid groups only.

The country effect for the ANOVA model will be accounted by country indicator variables that will be treated as continuous variable in order to obtain adjusted GMCs that reflect the distribution of subjects between countries.

Summaries planned per countries will be limited to the PPS. These summaries will also be generated by frequent race and by gender. Note that a race category is considered if it includes more than 40 subjects. Infrequent race categories will be combined together and summarized if it includes more than 40 subjects.

## **6.4. Analysis of safety**

### **6.4.1. Analysis of safety planned in the protocol**

The ES will be used for the analysis of safety.

The following calculations will be performed for each group and for the pooled liquid vaccine group:

The percentage of doses and of subjects reporting at least one symptom (solicited or unsolicited) during the 8 days (Day 0-Day 7) solicited follow-up period post vaccination will be computed, along with exact 95% CI. The same calculations will be done for symptoms (solicited or unsolicited) rated as grade 3 in intensity and for symptoms (solicited or unsolicited) assessed as causally related to vaccination.

The percentage of doses and of subjects reporting each individual solicited general symptom will be computed, over the 8 days (Day 0-Day 7) solicited follow-up period post vaccination, along with exact 95% CI. The same calculations will be done for each individual general solicited symptom rated as grade 3 in intensity, for each individual solicited general symptom assessed as causally related to vaccination and those that resulted in a medically attended visit.

The verbatim reports of unsolicited AEs will be reviewed by a physician and the signs and symptoms will be coded according to MedDRA. Every verbatim term will be matched with the appropriate Preferred Term. The percentage of subjects with unsolicited AEs occurring within 31 days (Day 0-Day 30) follow-up period after any dose with its exact 95% CI will be tabulated by group, and by preferred term. Similar tabulation will be done for unsolicited AEs rated as grade 3, for unsolicited AEs with causal relationship to vaccination and those that resulted in a medically attended visit.

The percentage of subjects reporting GE episodes from Dose 1 of HRV vaccine up to Visit 3 will be tabulated by group.

The percentage of subjects with presence of RV in GE stool samples collected from Dose 1 of HRV vaccine up to Visit 3 will be tabulated by group.

The percentage of GE episodes with no available stool results from Dose 1 of HRV vaccine up to Visit 3 will be tabulated.

The percentage of subjects who started taking at least one concomitant medication from HRV vaccination to Day 7 after vaccinations will be tabulated with exact 95% CI. The percentages of subjects who started taking at least one concomitant medication during the study period will be tabulated with exact 95% CI.

SAEs reported during the study period will be described in detail.

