## SYNOPSIS

Detailed Title	A phase IIIA, randomised, observer-blind, multi-centre study to evaluate the clinical consistency of three production lots of the Porcine circovirus (PCV)-free liquid formulation of GlaxoSmithKline (GSK) Biologicals' oral live attenuated human rotavirus (HRV) vaccine and to evaluate the PCV-free liquid formulation of GSK Biologicals' HRV vaccine as compared to the currently licensed lyophilised formulation of the HRV vaccine in terms of immunogenicity, reactogenicity and safety when administered as a two-dose vaccination in healthy infants starting at age 6-12 weeks.
Indication	Active immunisation of infants against gastroenteritis (GE) due to rotavirus (RV).

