#### 10.8.1. Within groups assessment

The following calculations will be performed for each group and for the pooled liquid vaccine group:

The percentage of doses and of subjects reporting at least one symptom (solicited or unsolicited) during the 8 days (Day 0-Day 7) solicited follow-up period post vaccination will be computed, along with exact 95% CI. The same calculations will be done for symptoms (solicited or unsolicited) rated as grade 3 in intensity and for symptoms (solicited or unsolicited) assessed as causally related to vaccination.

The percentage of doses and of subjects reporting each individual solicited general symptom will be computed, over the 8 days (Day 0-Day 7) solicited follow-up period post vaccination, along with exact 95% CI. The same calculations will be done for each individual general solicited symptom rated as grade 3 in intensity, for each individual solicited general symptom assessed as causally related to vaccination and those that resulted in a medically attended visit.

The verbatim reports of unsolicited AEs will be reviewed by a physician and the signs and symptoms will be coded according to MedDRA. Every verbatim term will be matched with the appropriate Preferred Term. The percentage of subjects with unsolicited AEs occurring within 31 days (Day 0-Day 30) follow-up period after any dose with its exact 95% CI will be tabulated by group, and by preferred term. Similar tabulation will be done for unsolicited AEs rated as grade 3, for unsolicited AEs with causal relationship to vaccination and those that resulted in a medically attended visit.

The percentage of subjects reporting GE episodes from Dose 1 of HRV vaccine up to Visit 3 will be tabulated by group.

The percentage of subjects with presence of RV in GE stool samples collected from Dose 1 of HRV vaccine up to Visit 3 will be tabulated by group.

The percentage of GE episodes with no available stool results from Dose 1 of HRV vaccine up to Visit 3 will be tabulated.

The percentage of subjects who started taking at least one concomitant medication from HRV vaccination to Day 7 after vaccinations will be tabulated with exact 95% CI. The percentages of subjects who started taking at least one concomitant medication during the study period will be tabulated with exact 95% CI.

SAEs reported during the study period will be described in detail.

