#### 3.2. Secondary

##### Reactogenicity and safety

- To evaluate the reactogenicity of the liquid HRV vaccine and currently licensed lyophilised HRV vaccine in terms of solicited AEs during the 8 days (Day 0-Day 7) follow-up period after each vaccination.
- To assess the safety of the study vaccines in terms of unsolicited AEs during the 31 days (Day 0-Day 30) follow-up period after each vaccination and Serious Adverse Events (SAEs) during the entire study period.

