## **6. STATISTICAL ANALYSES**

Note that standard data derivation rule and stat methods are described in [Annex 1](#) and will not be repeated below. All Confidence Interval (CI) will be two-sided 95% CI.

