#### **6.3.1.2. Between groups assessment**

- The 95% CI for the ratio of anti-RV IgA antibody GMCs at Visit 3 between any pair of the three lots of the HRV liquid vaccine will be computed (first co-primary objective).
- The asymptotic standardized 95% CI for the difference in seroconversion rate at Visit 3 between the PCV-free liquid HRV vaccine (pooled HRV liquid groups) and lyophilised HRV vaccine will be computed (second co-primary objective).
- The 95% CI for the ratio of anti-RV IgA antibody GMCs at Visit 3 between the PCV-free liquid HRV vaccine (pooled HRV liquid groups) and lyophilised HRV vaccine will be computed (third co-primary objective).

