## 11. ANNEX 1 STANDARD DATA DERIVATION RULE AND STATISTICAL METHODS

### 11.1. Statistical Method References

The exact two-sided 95% CIs for a proportion within a group will be the Clopper-Pearson exact CI Clopper CJ, Pearson ES. The use of confidence or fiducial limits illustrated in the case of binomial. *Biometrika*. 1934;26:404-413.

The standardised asymptotic two-sided 95% CI for the group difference in proportions is based on the method described in the following paper: Robert G. Newcombe, interval estimation for the difference between independent proportions: comparison of eleven methods, *Statist Med*. 1998; 17, 873-890. The standardised asymptotic method used is the method six.

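### The title promises a comparison of liquid with lyophilised vaccine on reactogenicity and safety, but the plan never estimates that difference or its precision

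*SAP*

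**What the plan says.** The Detailed Title in the protocol synopsis names the comparison: liquid vaccine "as compared to the currently licensed lyophilised formulation of the HRV vaccine in terms of immunogenicity, reactogenicity and safety". The matching secondary objective (SAP 3.2) is softer: "To evaluate the reactogenicity of the liquid HRV vaccine and currently licensed lyophilised HRV vaccine in terms of solicited AEs", with no hypothesis and no margin.

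Protocol 10.8 has a single analysis subsection, "10.8.1. Within groups assessment". SAP 6.4.1 repeats it, opening with "The following calculations will be performed for each group and for the pooled liquid vaccine group", and SAP 6.4.2 adds further per-group summaries. The within-group method is stated in SAP 11.1: "The exact two-sided 95% CIs for a proportion within a group will be the Clopper-Pearson exact CI".

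Immunogenicity is handled differently. SAP 6.3.1.2 plans "The asymptotic standardized 95% CI for the difference in seroconversion rate at Visit 3 between the PCV-free liquid HRV vaccine" and the lyophilised group, and SAP 11.1 fixes how: "The standardised asymptotic method used is the method six". That method is not applied to any safety outcome.

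The mock tables follow the text. Template 20 sets pooled liquid beside Lyo for each solicited symptom, with separate exact intervals and no difference column. Template 24 does the same for gastroenteritis (GE). No listed template title is a between-group safety table. The secondary endpoint of 90 U/mL or more also gets only per-group intervals (SAP 6.3.1.1).

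**The concern.** The safety question for a reformulated vaccine is how it differs from the licensed product. The quantity that answers it is the difference in rates with its interval, and the plan does not produce it. A reader of the study report would have two percentages, each with its own interval, and no statement of how large a difference the data could rule out.

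Separate intervals are a poor substitute. Two 95% intervals fail to overlap only when the difference exceeds roughly 1.96 × (SE1 + SE2). The 95% interval of the difference excludes 0 from roughly 1.96 × √(SE1² + SE2²). Anyone who compares the intervals by eye is therefore applying a stricter criterion than the usual one. If the contrast is instead worked out later from the printed counts, the choice of rows becomes post hoc.

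**Working it through.** **Inputs.** Planned safety numbers: 3 × 400 = 1200 liquid and 400 Lyo (Protocol 10.3). Confidence level: "All Confidence Interval (CI) will be two-sided 95% CI" (SAP 6). Illustrative counts: the SAP mock tables, which SAP Annex 3 says were copied from ROTA-061. The documents state no expected safety rates, so the rates in steps 3 and 4 are assumptions.

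**1. Reproduce the plan's own figures.**
- Template 24, GE from Dose 1 to before Dose 2, Clopper-Pearson: 50/900 = 5.6% (4.2 to 7.3) and 8/300 = 2.7% (1.2 to 5.2), as printed.
- Template 13, seroconversion, Lyo minus liquid, 228/252 against 661/746. The score limits are the values δ at which |p1 − p2 − δ| / √(v1 + v2) = 1.96, where v1 and v2 are binomial variances at the maximum-likelihood rates constrained to differ by δ. Result: −2.85 to 5.83, as printed (upper limit 5.84 with the Miettinen-Nurminen variance factor).

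**2. Apply the same method to safety rows in the shells.**

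| Row | Liquid | Lyo | Difference, points (95% CI) |
|---|---|---|---|
| GE, Dose 1 to before Dose 2 | 50/900 (4.2–7.3) | 8/300 (1.2–5.2) | +2.89 (0.10 to 5.09) |
| GE, Dose 2 to Visit 3 | 43/898 (3.5–6.4) | 15/299 (2.8–8.1) | −0.23 (−3.55 to 2.32) |
| GE, Dose 1 to Visit 3 | 87/900 (7.8–11.8) | 22/300 (4.7–10.9) | +2.33 (−1.58 to 5.60) |
| Grade 3 cough/runny nose, Dose 1 | 2/900 (0.0–0.8) | 4/300 (0.4–3.4) | −1.11 (−3.17 to −0.16) |

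In the first and last rows the separate intervals overlap although the difference interval excludes 0. That shows the mechanism and nothing more. The same interval on the 36 pooled-liquid versus Lyo rows of Template 20, three each of Templates 24 and 25, and three of Template 18 (Dose 1, Dose 2, overall per subject) excludes 0 in only these 2 of 45. Under no difference, about 45 × 0.05 = 2.25 would be expected, though the rows are correlated. The two also point in opposite directions.

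**3. Precision at the planned size.** Half-width = 1.96 × √[p(1 − p)(1/1200 + 1/400)].
- p = 0.70: 1.96 × √(0.21 × 0.003333) = 5.2 points.
- p = 0.03: 1.96 × √(0.0291 × 0.003333) = 1.9 points.

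**4. How much stricter overlap is at 1200 against 400.** With equal rates, SE2 = √3 × SE1, so the ratio of the two thresholds is (1 + 1.732)/2 = 1.37. With the actual interval methods:

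| Assumed Lyo rate | Difference CI excludes 0 from | Exact CIs separate from |
|---|---|---|
| 5% | +3.00 points | +4.25 points |
| 20% | +4.83 points | +6.75 points |
| 50% | +5.67 points | +7.92 points |

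In 20,000 simulated trials at assumed true rates of 5.6% and 2.7%, the difference interval excluded 0 in 68% and the separate intervals were disjoint in 37%. In 31% the intervals overlapped although the difference interval excluded 0.

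**The case against.** The strongest reply is that nothing here is wrong. The safety objectives speak of evaluating and assessing, and Protocol 10.9 and SAP 7 declare everything outside the co-primaries descriptive or exploratory. Templates 20 and 24 print both numerators and denominators, so anyone can compute the difference. All of this stands, and it limits the point to a gap in reporting. Descriptive status removes the need for a test. It does not remove the value of estimating the contrast that the title names.

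A reader might infer that the plan will judge similarity by overlapping intervals and so leans towards finding no difference. The documents do not support that: no section adopts overlap as a rule, and step 4 describes a habit that readers may bring to the tables.

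A reader might also infer from step 2 that the liquid formulation causes more GE. The shells do not support that either. They hold figures from another study, given for illustration, and the two striking rows are about as many as chance would give.

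The exact list matters too. GE up to Visit 3 alone would not have shown the Dose 1 to Dose 2 contrast. Per-subject reporting alone would not have shown the cough row: liquid is 3 + 2 + 5 = 10/900 (Template 21) and Lyo at most 4 + 2 = 6/300 (Template 20). Even at 6/300, z = 0.0089 / √[0.01333 × 0.98667 × (1/900 + 1/300)] ≈ 1.2.

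For the 90 U/mL endpoint, the seroconversion difference and GMC ratio already give between-group inference on the same assay, so that addition is optional.

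**Conclusion.** The gap holds. The title sets reactogenicity and safety as points of comparison with the lyophilised vaccine, and neither the protocol, the SAP text nor the listed template titles provide an estimate of that comparison. Some template bodies were not available for review, so for those the conclusion rests on their titles.

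No confirmatory conclusion, sample-size figure or error rate is affected. What is lost is the precision of the contrast, about ±5.2 points for a symptom at 70% and ±1.9 points for one at 3%, under assumed rates common to both groups. The change is worth making, but the study does not depend on it.

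**What to change.** Add one paragraph to SAP 6.4.2. No protocol amendment is needed, because that section already adds safety summaries beyond the protocol. Give the asymptotic standardised (method six) 95% CI for pooled liquid minus Lyo, on the Exposed Set, for:

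- each solicited symptom, any and grade 3, after Dose 1, after Dose 2 and per subject overall;
- at least one unsolicited AE in the Day 0–Day 30 window;
- GE in each of the three periods of Template 24;
- at least one SAE from Dose 1 to study end;
- optionally, the percentage at or above 90 U/mL, on the Per-Protocol Set.

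State that there is no margin, no test and no multiplicity adjustment. The safety list has 6 × 2 × 3 + 1 + 3 + 1 = 41 intervals, so at about 1 in 20 some two may exclude 0 by chance (41 × 0.05 = 2.05); the SAP should say so beside the tables.

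The cost is the SAP wording and a difference column in the affected templates, using a method already specified for the second co-primary. The downside is that an isolated interval excluding 0 may be over-read, which the exploratory label in SAP 7 and the fixed list are there to contain.

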#### 6.4.2. Additional considerations

As indicated in section 10.5 of the protocol and in line with the project history, analysis of safety will be primarily performed per dose administered and subjects who missed reporting symptoms (solicited/unsolicited or concomitant medications) will be treated as subjects without symptoms (solicited/unsolicited or concomitant medications, respectively). A sensitivity analysis will be performed on documented doses i.e. accounting only for doses where solicited symptoms are indicated as being absent/present in case more than 5% of the doses are not documented.

Summary of temperature will be provided by 0.5° increment (i.e.  $\geq 38.0^{\circ}\text{C}$ ,  $>38.5$ ;  $> 39$ ,  $> 39.5$ ,  $> 40$ ).

Gastroenteritis is assumed to take place when either:

- a stool collection is reported
- three or more than 3 loose stools are reported as solicited diarrhoea symptom.
- an unsolicited symptom, which has an onset date more than 7 days after vaccination (i.e. with onset day  $> 8$ ), is associated with the high lever MedDRA terms hereunder but excluding Diarrhoea as primary preferred term (10012735): ‘Gastric and gastroenteric infections’ (10017887), ‘Gastrointestinal infections, site unspecified’ (10017968), ‘Intestinal infections (10022678)’, ‘Faecal, abnormalities NEC’ (10016097), ‘Diarrhoea (excl infective)’ (10012736).

Summary of solicited symptoms will also be provided by country, gender and frequent race(s) while summary of unsolicited symptoms within 31 days post-vaccination will be provided by country – see section 6.3.2 for the definition of frequent race.

Summary of solicited symptoms will also be provided for each individual general solicited symptom causally related to vaccination and rated as grade 3 in intensity. Likewise the percentage of subjects and of doses with grade 3 causally related unsolicited AEs occurring within 31 days (Day 0-Day 30) follow-up period after any dose with its exact 95% CI will be tabulated by group, and by preferred term. These summaries will not be provided by country, gender or frequent race(s).

[figure not shown]
Note that the study will be converted in cDISC. Accordingly Day 0-Day 7 and Day 0-Day 30 will be replaced by Day 1-Day 8 and Day 1-Day 31 for the statistical analysis.

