### Reactogenicity and safety:

- Subjects who missed reporting symptoms (solicited/unsolicited or concomitant medications) will be treated as subjects without symptoms (solicited/unsolicited or concomitant medications, respectively).

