### **5.3. Important protocol deviation not leading to elimination from per-protocol analysis set**

The following important protocol deviations will be reported by groups:

- Forced randomization: In case of supplies shortage for the next assigned vaccine according to the randomization schedule at the clinical site, the randomization system will use the forced randomization procedure in order to continue to enrol and vaccinate subjects. The system moves seamlessly to the next treatment/randomization number for which vaccine supplies are available. The site will not be aware of the forced randomization event.
- Manual randomization: In case the randomization system is unavailable, the investigator has the option to perform randomization by selecting supplies available at the site according to a pre-defined rule. In case the randomization system is available, a vaccine different from the randomized treatment may have been administered at dose 1.
- Short follow-up: subjects with a safety follow-up period after the last dose of HRV vaccine that is less than 180 days.
- Vaccinated subjects without documentation of solicited symptoms i.e. for a vaccine dose administered, at least one solicited symptom is not documented as being present or absent.

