#### 11.1.5. Safety

- For analysis of solicited, unsolicited adverse events (such as serious adverse events or adverse events by primary MedDRA term) and for the analysis of concomitant medications, all vaccinated subjects will be considered. Subjects who did not report the event or the concomitant medication will be considered as subjects without the event or the concomitant medication respectively.
- In case there will be more than 5% of subjects without documented dose for solicited symptoms (i.e., symptom screen not completed), sensitivity analysis will include only vaccinated subjects for doses with documented safety data (i.e., symptom screen completed).

- The following rules will be used for the analysis of solicited symptoms:
  - Subject who didn't document the presence or absence of a solicited symptom after one dose will be considered not having that symptom after that dose in the analysis done on "administrated dose"
  - Subjects who documented the absence of a solicited symptom after one dose will be considered not having that symptom after that dose.
  - Subjects who documented the presence of a solicited symptom and fully or partially recorded daily measurement over the solicited period will be included in the summaries at that dose and classified according to their maximum observed daily recording over the solicited period.
  - Subjects who documented the presence of a solicited symptom after one dose without having recorded any daily measurement will be considered as having that symptom after that dose).

- For the analysis, temperatures will be coded as follows for oral, axillary or tympanic route:

Grade	Temperature
0	< 38.0°C
1	≥ 38.0°C - < 38.5°C
2	> 38.5°C - < 39.5°C
3	> 39.5°C

- Note that for all tables described in this section, the way the percentage of subjects will be derived will depend on the event analysed (see table below for details). As a result, the N value will differ from one table to another.

Event	N used for deriving % per subject for Vaccination phase	N used for deriving % per dose for Vaccination phase
Concomitant vaccination	All subjects with study vaccine administered	All study visits with study vaccine administered

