Solicited general symptom	Primary analysis: all subjects with study vaccine administered Sensitivity analysis as applicable (see section 6.4.2): all subjects with at least one solicited general symptom documented as either present or absent (i.e., symptom screen completed)	Primary analysis: all study visits with study vaccine administered Sensitivity analysis: all study visits with study vaccine administered and with at least one solicited general symptom documented as either present or absent (i.e., symptom screen completed)
Unsolicited symptom	All subjects with study vaccine administered	All study visits with study vaccine administered
Concomitant medication	All subjects with study vaccine administered	All study visits with study vaccine administered

For summaries by MedDRA primary preferred term combining solicited and unsolicited adverse events, solicited adverse events will be coded as per the following MedDRA codes

Solicited symptom	Lower level term code	Corresponding Lower level term decode
Fever	10016558	Fever
Irritability/Fussiness	10022998	Irritability
Diarrhoea	10012727	Diarrhoea
Vomiting	10047700	Vomiting
Loss of appetite	10003028	Appetite lost
Cough/runny nose	10011224	Cough

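### The main reactogenicity tables count undocumented solicited symptoms as absent, and the documented-dose check on this is conditional and loosely defined

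*SAP*

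**What the plan says.** **Main analysis.** Protocol 10.5 sets the rule: "Subjects who missed reporting symptoms (solicited/unsolicited or concomitant medications) will be treated as subjects without symptoms". SAP 6.4.2 repeats it: "subjects who missed reporting symptoms (solicited/unsolicited or concomitant medications) will be treated as subjects without symptoms". SAP 11.1.5 applies it symptom by symptom ("Subject who didn't document the presence or absence of a solicited symptom after one dose will be considered not having that symptom") but confines that sentence to the analysis of administered doses. The per-subject denominator in the SAP 11.1.5 table is "Primary analysis: all subjects with study vaccine administered"; the per-dose denominator is every visit at which study vaccine was given.

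**Back-up analysis.** SAP 6.4.2 plans a sensitivity analysis on documented doses "in case more than 5% of the doses are not documented". SAP 11.1.5 states the same 5% threshold as a share of subjects. The per-subject denominator is "all subjects with at least one solicited general symptom documented as either present or absent (i.e., symptom screen completed"; the per-dose denominator is "all study visits with study vaccine administered and with at least one solicited general symptom documented as either present or absent".

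**Reporting of gaps.** SAP 5.3 lists as an important deviation a vaccinated subject for whom "at least one solicited symptom is not documented as being present or absent" after a dose. SAP 6.1.2 plans that summary for the PPS. Template 17 tabulates symptom-sheet return by group and dose, with no threshold.

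**The concern.** An infant whose diary is missing cannot enter the numerator but stays in the denominator. The rule can lower a reported rate and cannot raise it. The exact confidence intervals do not reflect this, because they treat the missing dose as an observed negative.

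Reactogenicity of the liquid and lyophilised vaccines is a secondary objective. If diary completion differed between groups, the tables would show a difference that comes from paperwork. The safeguard is the documented-dose analysis, so it matters whether that analysis will appear and whether its denominator removes the problem.

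**Working it through.** **1. Mechanism, from the plan's own mock tables (ROTA-061 data).** For Liq_A, Dose 2, cough/runny nose, Template 19 (administered doses) gives 92/297 = 31.0% (exact 95% CI 25.8 to 36.6). Template 28 (documented doses) gives 92/296 = 31.1% (25.9 to 36.7). Both intervals reproduce with the Clopper-Pearson method. The numerator is the same; the one unreturned sheet is a negative in Template 19 and absent from Template 28.

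**2. Size in the main analysis.** Let u be the undocumented share, p_d the rate among documented doses and p_u the rate among undocumented doses.

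- True rate = p_d(1 − u) + p_u·u
- Reported rate = p_d(1 − u)
- Bias = −p_u·u, which is never positive

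The documents give no u for this trial. Assuming p_u = p_d = p, for rates close to irritability, loss of appetite and diarrhoea at Dose 1 in Template 20:

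| u | p = 70% | p = 25% | p = 2.8% |
|---|---|---|---|
| 0.5% | 69.65% | 24.88% | 2.79% |
| 5% | 66.5% | 23.75% | 2.66% |
| 10% | 63.0% | 22.5% | 2.52% |

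In Template 17, sheets are missing for 2 of 1798 liquid doses and 3 of 599 Lyo doses. Together that is 5/2397 = 0.21%, and 70% × 0.21% = 0.15 point. For Lyo alone, 3/599 = 0.5%, and 70% × 0.5% = 0.35 point. At the 5% threshold the loss is 70% × 5% = 3.5 points.

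**3. Trigger.** The planned 1600 infants give 3200 doses, 800 per group. If the 5% is taken over the whole trial, 0.05 × 3200 = 160 missing doses do not exceed it. In the extreme case that all 160 fall in one group, 160/800 = 20%, and a 70% rate there reads 70% × 0.80 = 56% with no sensitivity analysis. Read per group, this cannot happen. The SAP does not say which reading applies.

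**4. Denominator of the back-up.** Take an infant with fever recorded and diarrhoea blank.

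- Under SAP 5.3 this is an important deviation, because one symptom is undocumented.
- Under the SAP 11.1.5 table the infant is documented, because one symptom is recorded.
- Template 28 uses one N for all six symptoms within a dose. At Dose 2 these are 296, 301 and 299, exactly the sheets returned in Template 17. So this infant would stay in the diarrhoea denominator with no way into the numerator.
- Per subject, one symptom recorded at either dose is enough to stay in N.
- If one entry makes a dose documented, partly filled screens also do not count towards the 5% trigger.

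If a share q of otherwise documented doses is blank for a symptom and the rate is the same in those doses, the back-up reports p(1 − q). For p = 70%, q = 2% gives 68.6% and q = 5% gives 66.5%. The documents give no q.

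**5. Documented-only rates are not assumption-free.** Their bias is u(p_d − p_u), which can have either sign. If symptomatic infants are twice as likely to be undocumented, with p = 70% and u = 5%, the missing probability is 0.05/1.70 = 2.94% without the symptom and 5.88% with it. The administered-dose rate is then 0.70 × 0.9412 = 65.9%, and the documented-dose rate is 0.659/0.95 = 69.3%.

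**The case against.** The rule is pre-specified in the protocol, and the SAP keeps it for consistency with the project's history. The endpoints are descriptive, and no test or interval for a liquid-versus-lyophilised difference in symptoms is planned. Protocol 5.6.14 requires unreturned diary cards to be sought. The only return rates in the documents are near 100%. If blanks come mainly from infants with nothing to report, counting them as absent is nearly right, and a documented-only rate would be too high. All of this stands, and it limits the size and consequence of the point.

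Two stronger readings are tempting and are not supported:

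- **That the back-up certainly repeats the imputation.** SAP 11.1.5 attaches the counted-as-absent sentence to the administered-dose analysis only, and its denominator table equates documented with a completed symptom screen. If completion requires all six entries, q is zero and nothing is imputed. The documents do not say so. The flaw is an inference from the at-least-one wording and the single N in Template 28.
- **That missing data below 5% are never shown.** Template 17 gives sheet return by group and dose unconditionally, and the SAP 5.3 deviation is reported by group for the PPS. A reader can bound the effect of whole-sheet loss. What is not planned is a count of blanks by symptom, or the SAP 5.3 count for the Exposed Set, on which safety is analysed.

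**Conclusion.** The point holds as a cheap improvement. The direction of the bias in the main tables is certain: downward or zero. Its size is unknown for this trial. It is about 0.1 point for a 70% symptom if missingness resembles the ROTA-061 mock data, and 3.5 points at 5% missing if undocumented infants have the same rate as documented ones. The 5% figure marks the edge of what the plan tolerates without a check; it is not a forecast.

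Three defects of wording are independent of size: the trigger has two units and no stated scope; documented is defined in opposite ways in SAP 5.3 and 11.1.5; and the back-up denominator leaves open whether a blank symptom counts as absent. A reader might also infer a threat to the licensure conclusions. There is none: the three co-primary immunogenicity objectives do not use these data.

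**What to change.** In SAP 6.4.2 and 11.1.5:

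1. Keep the administered-dose table for comparison with earlier studies.
2. Always report the documented-dose table, using for each symptom only the doses where that symptom is marked present or absent. The Template 28 shell exists but shows only the three liquid lots; add the pooled liquid and Lyo columns.
3. Use one definition of documented in SAP 5.3, 6.4.2 and 11.1.5.
4. Show undocumented counts by group, dose and symptom for the Exposed Set.

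Once the table is always reported, the 5% trigger and its conflicting units can be deleted.

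The cost is SAP wording and one extra set of tables. Because the documented-only rate assumes that missingness is unrelated to the symptom, show both tables side by side. Which one leads is a matter of preference.
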